5.9. Safety Set

The Safety Set consists of all enrolled (Part 1) or randomized (Part 2) participants who received at least one dose of IP. The Safety Set will be used for analysis of safety except for the solicited ARs. In addition, the following Safety Set is defined for each injection separately. The First Injection Safety Set consists of all subjects in the Safety Set who have received the first study injection. The Second Injection Safety Set consists of all subjects in the Safety Set who have received the second study injection. Participants will be included in the vaccination group corresponding to the vaccination they actually received. For a participant who was randomized to placebo in Part 2 but received any dose of mRNA-1273.214 at any injection, the participant will be included in the mRNA-1273.214 group in the Safety Set.

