5.10. Solicited Safety Set

The Solicited Safety Set consists of all participants in the safety set who contribute any solicited AR data, i.e., have at least one postbaseline solicited safety assessment. The Solicited Safety Set will be used for the analyses of solicited ARs and participants will be

included in the vaccination group corresponding to the study injection they actually received. In addition, the following Solicited Safety Set is defined for each injection separately.

The First Injection Solicited Safety Set consists of all subjects in the Solicited Safety Set who have received the first study injection and have contributed any solicited AR data from the time of first study injection through the following 6 days.

The Second Injection Solicited Safety Set consists of all subjects in the Solicited Safety Set who have received the second study injection and have contributed any solicited AR data from the time of second study injection through the following 6 days. Participants will be analyzed according to the vaccination group a participant received, rather than the vaccination group to which the subject was randomized. A participant who was randomized to placebo but received any dose of mRNA-1273.214 at any injection will be included in the mRNA-1273.214 group in the Solicited Safety Set.

6. Statistical Analysis

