- Imputation rules for missing AE dates are provided in Appendix D.
- For laboratory assessments, if majority of results are indefinite, imputation of these values will be considered. If the laboratory results are reported as below the LLOQ (e.g., <0.1), the numeric values will be imputed by 0.5 × LLOQ in the summary. If the laboratory results are reported as greater than the ULOQ (e.g., >3000), the numeric values will be imputed by ULOQ in the summary.
- Other incomplete/missing data will not be imputed, unless specified otherwise.

Treatment groups:

The following vaccination groups will be used for summary purposes:

- Part 1, Open-Label Phase:
 - o mRNA-1273.214 5 μg
 - o mRNA-1273.214 10 μg
 - o mRNA-1273.214 Total
- Part 2, Blinded Phase:

Treatment in Part 2 will be the selected dose level from Part 1 or Placebo

- o mRNA-1273.214 5 μg, or
- o mRNA-1273.214 10 μg

And

o Placebo

Subjects who received at least one dose of mRNA-1273.214 in Part 2 will be included in the mRNA-1273.214 selected dose level group (as actual treatment) in Part 2 in the safety and immunogenicity analyses.

External comparator:

• Comparator: mRNA-1273 100 μg primary series (from study P301 in young adult participants (18-25 years) who received 2 doses of mRNA-1273 primary series)

Summary by study part:

Separate shells will be provided for Part 1 and Part 2 of the study. All analyses and data summaries/displays will be provided by vaccination group.

Analysis Periods

The following analysis periods and treatment groups will be used for efficacy or immunogenicity analyses for Part 2, the blinded phase, unless specified otherwise:

Part 2 Group	Description	Part 2 Blinded Phase Analysis Period for Efficacy or Immunogenicity
mRNA-1273.214	Participants randomized to mRNA-1273.214 in the Blinded Phase	From randomization to earliest date of unblinding (inclusive), study

Diagram	Participants randomized to	discontinuation, study completion,
Placebo	Placebo in the Blinded Phase	death, and data cutoff date

The following analysis period and treatment groups will be used for safety analysis for Part 2, the blinded phase, unless specified otherwise:

Part 2 Group	Description	Part 2 Blinded Phase Analysis Period for Safety
mRNA-1273.214	Participants received at least one dose of mRNA-1273.214 in the Blinded Phase	From the date of first injection to the earliest date of unblinding (inclusive),

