Placebo	Participants only received Placebo in the Blinded Phase	study discontinuation, study completion, death, and data cutoff date

Subgroup Analysis

Safety, efficacy, and immunogenicity endpoints may be analyzed in select subgroups specified below as applicable:

- Sex (Female, Male)
- Baseline SARS-CoV-2 Status (Positive, Negative)
- Maternal COVID-19 vaccine status
- Maternal COVID-19 infection status
- Race
- Ethnicity

All analyses will be conducted using SAS Version 9.4 or higher.

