6.3.2. Solicited Adverse Reactions

An AR is any AE for which there is a reasonable possibility that the test product caused the AE. The term "Solicited Adverse Reactions" refers to selected signs and symptoms occurring after injection administration during a specified post-injection follow-up period (day of injection and 6 subsequent days). The solicited ARs are recorded by the subject in eDiary. The occurrence and intensity of selected signs and symptoms is actively solicited from the participant during a specified post-injection follow-up period (day of injection and 6 subsequent days), using a pre-defined checklist (i.e., solicited ARs).

The following local ARs will be solicited by the eDiary: pain/tenderness at injection site, erythema (redness) at injection site, swelling/induration (hardness) at injection site, and groin or underarm swelling or tenderness ipsilateral to the side of injection.

The following systemic ARs will be solicited by the eDiary: fever, irritability/crying, sleepiness, and loss of appetite.

The AR categories are presented in Table 7 in the protocol.

The solicited ARs will be graded based on the grading scales presented in Table 7 in the protocol, modified from the Toxicity Grading Scale for Healthy Adult and Adolescent Volunteers Enrolled in Preventative Vaccine Clinical Trials (DHHS 2007). Investigator will assess Grade 4 events (with exception of fever).

If a solicited local or systemic AR continues beyond 7 days post injection, the participant's parent(s)/ LAR(s) should notify the site to provide an end date to close out the event on the reactogenicity page of the eCRF.

All solicited ARs (local and systemic) will be considered causally related to injection.

Analyses of solicited ARs will be provided by study part and treatment group for each injection (first or second) based on the associated subset of Solicited Safety Set, i.e. First (Second) Injection Solicited Safety Set, unless otherwise specified.

The number and percentage of subjects who reported each individual solicited local AR (has a toxicity grade of Grade 1 or greater) and solicited systemic AR (has a toxicity grade of Grade 1 or greater) during the 7-day follow-up period after each injection will be tabulated by vaccination group, toxicity grade, and injection (i.e., first or second injection). The number and percentage of subjects who reported each individual solicited AR will also

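### Per-injection solicited reaction tables in Part 2 count a placebo diary as a vaccine diary when an infant has received one injection of each product

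*SAP*

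**What the plan says.** SAP 5.10 first gives a general as-treated rule: infants are "included in the vaccination group corresponding to the study injection they actually received". It then defines two subsets. The first reads "The First Injection Solicited Safety Set consists of all subjects in the Solicited Safety Set who have received the first study injection", provided that diary data exist for its 7-day window. The second reads "The Second Injection Solicited Safety Set consists of all subjects in the Solicited Safety Set who have received the second study injection", on the same condition. After the second definition comes the rule for mixed treatment: an infant randomised to placebo who "received any dose of mRNA-1273.214 at any injection will be included in the mRNA-1273.214 group in the Solicited Safety Set".

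SAP 6.1 applies the same convention to Part 2 safety generally. "Subjects who received at least one dose of mRNA-1273.214 in Part 2 will be included in the mRNA-1273.214 selected dose level group". The matching definition of the placebo group is "Participants only received Placebo in the Blinded Phase". SAP 5.9 has a parallel rule for the Safety Set: "received any dose of mRNA-1273.214 at any injection, the participant will be included in the mRNA-1273.214 group".

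SAP 6.3.2 sets the level of tabulation: "Analyses of solicited ARs will be provided by study part and treatment group for each injection (first or second"), using the corresponding subset. It also treats every solicited reaction as caused by the injection. Solicited reactions after each injection are a primary safety endpoint in both parts (SAP 3.1).

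**The concern.** A 7-day diary describes what followed one identified injection. The any-dose rule classifies it by the infant's whole exposure history, including doses given later. If an infant receives placebo on Day 1 and mRNA-1273.214 in error on Day 57, the Day 1 diary enters the first-injection vaccine column because of a product first given eight weeks afterwards.

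Protocol 2.3.2 reports that solicited reactions were more frequent on vaccine than on placebo in both Study P301 and Study P204. If that holds here, placebo diaries in the vaccine column lower its rate, which makes the vaccine look slightly better tolerated on a primary safety endpoint. The SAP foresees wrong-treatment cases: SAP 5.4 excludes them from the mITT-1 Set, and SAP 6.2.2 allows for infants vaccinated other than as randomised.

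**Working it through.** **Step 1: which column each diary enters.** Take a Part 2 infant with one injection of each product, and compare the SAP rule with grouping by the product given at that injection.

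| Order received | Table | Product behind the diary | Column under SAP 5.10 and 6.1 | Column by product at that injection |
|---|---|---|---|---|
| Placebo, then vaccine | First injection | Placebo | Vaccine | Placebo |
| Placebo, then vaccine | Second injection | Vaccine | Vaccine | Vaccine |
| Vaccine, then placebo | First injection | Vaccine | Vaccine | Vaccine |
| Vaccine, then placebo | Second injection | Placebo | Vaccine | Placebo |

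The two conventions differ in exactly one table per infant. SAP 5.10 covers the placebo-randomised infant. SAP 6.1 extends the same result to a vaccine-randomised infant given placebo once.

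**Step 2: size.** The plan states no figure on this point, so there is none to reproduce. Inputs:
- 300 infants per Part 2 arm (SAP 4.1), all assumed to contribute a diary.
- m, the number of mixed-treatment infants whose placebo diary belongs to the table in question. The documents give no misdosing rate, so m is an assumption.
- pv and pp, the reaction rates after a vaccine and a placebo injection. These are assumptions, taken as 70/50%, 50/20% and 80/30%.

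If m placebo-randomised infants are moved in, the vaccine-column rate is (300·pv + m·pp)/(300 + m). The shift from pv is −m(pv − pp)/(300 + m).

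| pv/pp | m = 1 | m = 3 |
|---|---|---|
| 70/50% | 0.20/301 = 0.07 points | 0.60/303 = 0.20 points |
| 50/20% | 0.30/301 = 0.10 points | 0.90/303 = 0.30 points |
| 80/30% | 0.50/301 = 0.17 points | 1.50/303 = 0.50 points |

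All shifts are downward. If instead m vaccine-randomised infants received placebo at that injection and stay in the column, the shift is −m(pv − pp)/300, which gives the same values to two decimals.

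**Step 3: ceiling.** The largest possible shift from one infant needs pv = 100% and pp = 0%: 1/301 = 0.33 points.

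**Step 4: scale.** At n = 300 and a rate of 50%, the 95% half-width by normal approximation is 1.96 × √(0.5 × 0.5/300) = 5.7 points. The planned Clopper-Pearson interval is slightly wider.

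**The case against.** **The text may only be ambiguous.** The any-dose sentence names the overall Solicited Safety Set, not its two subsets, and the general phrase in 5.10 refers to the injection actually received. A reader might infer that 5.10 contradicts itself outright, or that it already groups by injection. Neither is established. The general phrase does not mention mixed treatment, while the any-dose sentence addresses it directly, follows the subset definitions, and is repeated in 6.1. Read as general rule and special case, the sentences are compatible and the special case governs. What stands is that the phrase leaves room for a programmer to choose differently.

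**The any-dose rule has a purpose.** It keeps the placebo column free of vaccine-exposed infants. That is sound for events across the study and has some force at the second injection. It has none at the first, where an infant given placebo has had no vaccine.

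**It affects no data that the SAP describes.** Part 1 has no placebo, and SAP section 7 records an enrollment pause with 18 infants in Part 1 Arm 2. This stands as a limit on importance. The SAP nevertheless keeps the Part 2 analyses in full.

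**Nothing turns on the shift, and cases would be visible.** Solicited reactions are described with intervals, not tested. Injections given, major deviations and solicited reactions are all listed (SAP 6.2.5, 6.2.6, 6.3.2). This also stands, and supports the lowest priority.

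**SAP 5.9 has the same wording.** A reader might infer that its injection-specific Safety Sets misassign events too. No analysis in the SAP is assigned to those sets: unsolicited events use the periods in 6.1 with Safety Set denominators (6.3.1), and concomitant medications use the Safety Set (6.2.4).

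**Conclusion.** The point holds as a minor defect. Followed as written, SAP 5.10 with 6.1 and 6.3.2 puts one placebo diary per mixed-treatment infant into a per-injection vaccine column. The effect is zero unless Part 2 is run and an infant receives one injection of each product. Given that, one such infant lowers the vaccine rate at the affected injection by about 0.07 to 0.17 points and three by about 0.2 to 0.5, on 300 diaries and the assumed rates. The direction depends on placebo reactions being less frequent, as in the two earlier studies cited in the protocol.

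A reader might infer that vaccine reactogenicity would be materially understated, for instance by taking 0.33 points per infant as the expected shift. The documents do not support that. The 0.33 figure needs every vaccine diary to show a reaction and no placebo diary to do so, no misdosing rate is given, and the plausible shifts are far inside the interval around the estimate.

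**What to change.** In SAP 5.10, add that infants in the First and Second Injection Solicited Safety Sets are grouped by the product given at that injection. Keep the any-dose rule for solicited summaries across both injections and for all other safety analyses. In SAP 6.1, add a matching exception to the Part 2 any-dose sentence and to the placebo-only group definition; otherwise 5.10 and 6.1 would conflict. SAP 5.9 needs no change.

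The cost is two short text edits, with no new data and no design change, best made before any Part 2 unblinding. There is a small downside. An infant given vaccine first and placebo second would appear in the second-injection placebo column despite earlier vaccine exposure, so that column would no longer be strictly placebo-only. Footnote any such infant in the table. Group sizes may also differ slightly between the per-injection and overall tables, which the same footnote can explain.

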6.1. General Considerations

The Schedule of Assessments is provided in Appendix E for Part 1 and 2.

Continuous variables will be summarized using the following descriptive summary statistics: the number of subjects (n), mean, standard deviation (SD), median, minimum (min), and maximum (max). For the summary statistics of all numerical variables unless otherwise specified, the display precision will follow programming standards. Please see Appendix A for variable display standards.

Categorical variables will be summarized using counts and percentages. When count data are presented, the percentage will be suppressed when the count is zero in order to draw attention to the non-zero counts. A row denoted "Missing" will be included in count tabulations where specified on the shells to account for dropouts and missing values. The denominator for all percentages will be the number of subjects in that vaccination group within the analysis set of interest, unless otherwise specified.

Baseline value, unless specified otherwise, is defined as the most recent non-missing measurement (scheduled or unscheduled) collected before the first dose of IP. For immunogenicity tests and nasal swab tests, the baseline is defined as the most recent non-missing measurement (scheduled or unscheduled) collected before or on the date of first dose of IP (Day 1) prior to the first dose of IP.

Baseline SARS-CoV-2 status is determined by using virologic and serologic evidence of SARS-CoV-2 infection on or before Day 1.

Positive SARS-CoV-2 status at Baseline is defined as a positive RT-PCR test for SARS-CoV-2, and/or a positive serology test based on bAb specific to SARS-CoV-2 nucleocapsid on or before Day 1.

Negative status at Baseline is defined as a negative RT-PCR test for SARS-CoV-2 and a negative serology test based on bAb specific to SARS-CoV-2 nucleocapsid on or before Day 1.

Study day relative to the first injection will be calculated as below:

- a) study day prior to the first injection will be calculated as: date of assessment/event
 date of the first injection;
- b) study day on or after the date of the first injection will be calculated as: date of assessment/event date of the first injection + 1

Study day relative to the most recent injection will be calculated as below:

- a) study day prior to the first injection will be calculated as: date of assessment/event
 date of the first injection;
- b) study day on or after the date of the first injection but before the second injection (if applicable) will be calculated as: date of assessment/event date of the first injection + 1;
- c) study day on or after the date of the second injection will be calculated as: date of assessment/event date of the second injection + 1; if study day is on the same day as the second injection, date and time will be compared with the second injection date and time. If time is prior to the time of second injection, then study day is calculated as: date of assessment/event date of the first injection + 1; If it is after the time of second injection or the time is missing or not available then study day is calculated as: date of assessment/event date of the second injection + 1.

For calculation regarding antibody levels/concentrations, antibody values reported as below LLOQ will be replaced by 0.5 × LLOQ. Values that are greater than the upper limit of quantification (ULOQ) will be converted to the ULOQ if actual values are not available, and actual values will be used if available. Missing results will not be imputed.

The following analysis periods or stages for safety analyses will be used in this study:

- Up to 28 days after any vaccination: this stage starts at the day of each vaccination and continue through the earliest date of (the day of each vaccination and 27 subsequent days, next vaccination [if applicable]). This analysis period will be used as the primary analysis period for safety analyses including unsolicited AE, except for solicited AR, unless specified otherwise.
- Overall period (throughout the study): this analysis period starts at the first injection on Day 1 and continues through the earliest date of (study completion, discontinuation from the study, or death).

Unscheduled visits: Unscheduled visit measurements will be included in analysis as follows:

- In scheduled visit windows per specified visit windowing rules.
- In the derivation of baseline/last on-treatment measurements.
- In the derivation of maximum/minimum on-treatment values and maximum/minimum change from baseline values for safety analyses.
- In individual subject data listings as appropriate.

Visit windowing rules: The analysis visit windows for protocol-defined visits are provided in Appendix B.

Incomplete/missing data:

- Imputation rules for missing prior/concomitant medications, non-study vaccinations and procedures are provided in Appendix C.
- Imputation rules for missing AE dates are provided in Appendix D.
- For laboratory assessments, if majority of results are indefinite, imputation of these values will be considered. If the laboratory results are reported as below the LLOQ (e.g., <0.1), the numeric values will be imputed by 0.5 × LLOQ in the summary. If the laboratory results are reported as greater than the ULOQ (e.g., >3000), the numeric values will be imputed by ULOQ in the summary.
- Other incomplete/missing data will not be imputed, unless specified otherwise.

Treatment groups:

The following vaccination groups will be used for summary purposes:

- Part 1, Open-Label Phase:
 - o mRNA-1273.214 5 μg
 - o mRNA-1273.214 10 μg
 - o mRNA-1273.214 Total
- Part 2, Blinded Phase:

Treatment in Part 2 will be the selected dose level from Part 1 or Placebo

- o mRNA-1273.214 5 μg, or
- o mRNA-1273.214 10 μg

And

o Placebo

Subjects who received at least one dose of mRNA-1273.214 in Part 2 will be included in the mRNA-1273.214 selected dose level group (as actual treatment) in Part 2 in the safety and immunogenicity analyses.

External comparator:

• Comparator: mRNA-1273 100 μg primary series (from study P301 in young adult participants (18-25 years) who received 2 doses of mRNA-1273 primary series)

Summary by study part:

Separate shells will be provided for Part 1 and Part 2 of the study. All analyses and data summaries/displays will be provided by vaccination group.

Analysis Periods

The following analysis periods and treatment groups will be used for efficacy or immunogenicity analyses for Part 2, the blinded phase, unless specified otherwise:

Part 2 Group	Description	Part 2 Blinded Phase Analysis Period for Efficacy or Immunogenicity
mRNA-1273.214	Participants randomized to mRNA-1273.214 in the Blinded Phase	From randomization to earliest date of unblinding (inclusive), study

Diagram	Participants randomized to	discontinuation, study completion,
Placebo	Placebo in the Blinded Phase	death, and data cutoff date

The following analysis period and treatment groups will be used for safety analysis for Part 2, the blinded phase, unless specified otherwise:

Part 2 Group	Description	Part 2 Blinded Phase Analysis Period for Safety
mRNA-1273.214	Participants received at least one dose of mRNA-1273.214 in the Blinded Phase	From the date of first injection to the earliest date of unblinding (inclusive),
Placebo	Participants only received Placebo in the Blinded Phase	study discontinuation, study completion, death, and data cutoff date

Subgroup Analysis

Safety, efficacy, and immunogenicity endpoints may be analyzed in select subgroups specified below as applicable:

- Sex (Female, Male)
- Baseline SARS-CoV-2 Status (Positive, Negative)
- Maternal COVID-19 vaccine status
- Maternal COVID-19 infection status
- Race
- Ethnicity

All analyses will be conducted using SAS Version 9.4 or higher.

6.2. Background Characteristics

6.2.1. Subject Disposition

The number and percentage of subjects in the following categories will be summarized by study part and vaccination group as defined in Section 6.1 and baseline SARS-CoV-2 status based on the Full Analysis Set for Part 1 and Randomization Set for Part 2:

• Randomization Set (Part 2)

- Full Analysis Set (Part 1 and Part 2)
- Per-Protocol (PP) Set (Part 1 and Part 2)
- Immunogenicity Subset (Part 1 and Part 2)
- Per-Protocol Immunogenicity Subset (PPIS) (Part 1 and Part 2)
- PPIS Neg (Part 1 and Part 2)
- Safety Set (Part 1 and Part 2)
- Solicited Safety Set (Part 1 and Part 2)
- mITT Set (Part 1 and Part 2)
- mITT-1 Set (Part 1 and Part 2)

The percentage will be based on subjects in that vaccination group within the Full Analysis Set for Part 1 and in that vaccination group within the Randomization Set (as randomized) for Part 2, except the Solicited Safety Set and Safety Set for which the percentages will be based on the vaccination group in the Safety Set (as treated).

The number of subjects in the following categories will be summarized based on subjects screened:

- Number of subjects screened
- Number and percentage of screen failure subjects and the reason for screen failure

The percentage of subjects who screen failed will be based on the number of subjects screened. The reason for screen failure will be based on the number of subjects who screen failed.

The number and percentage of subjects in each of the following disposition categories will be summarized by vaccination group based on Full Analysis Set for Part 1 and summarized by vaccination group based on the Randomization Set for Part 2:

- Received each dose of IP
- Prematurely discontinued before receiving the second dose of IP and the reason for discontinuation
- Completed study
- Prematurely discontinued the study and the reason for discontinuation

A subject disposition listing will be provided, including informed consent, subjects who completed the study injection schedule, subjects who completed study, subjects who discontinued from study vaccine or who discontinued from participation in the study, with reasons for discontinuation. A separate listing will be provided for screen failure subjects with reasons for screen failure.

A subject who completed 12 months of follow up after the last injection received is considered to have completed the study.

